## 5.3 Analysis Plan for Primary Objectives

The objective of the primary endpoint analysis will be to demonstrate that treatment with adalimumab improves functioning as measured by the HAQ DI score in subjects with RA following treatment initiation (i.e. baseline).

- The changes in HAQ DI score at 12 and 24 weeks after the initiation of adalimumab will be presented (Excel Table 3.1); these changes will be summarized as the mean, SD, minimum, maximum, median, 95% confidence interval; as well as the number and percent of patients achieving a clinically meaningful improvement on the HAQ DI, as defined by a -0.22 point improvement or greater. In addition, the mean change will be tested with a paired t-test without adjusting for baseline disease severity, shown by p-value1; for sensitivity analysis, the mean change will be analyzed using ANOVA adjusting for baseline disease severity, shown by p-value2 in the table.
- The change in HAQ DI score at 24 weeks after the initiation of adalimumab (mean, SD, minimum, maximum, median, 95% confidence interval), in those patients continuing on adalimumab (responder population) will be compared with those patients not continuing on adalimumab (non-responders). The mean

changes in these two groups will be compared using an independent t-test with p-value listed in the table (Excel Table 3.2).

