9.5 Study Size

Approximately 89 patients diagnosed with RA will be recruited. The sample size was calculated by assuming an alpha of 0.05 and a power of 0.80 in a one-sided test, $Z(1-\alpha) = 1.645$ and $Z(1-\beta) = 0.842$. As to the primary variable, assuming a mean Δ HAQ-DI of -0.21 and a standard deviation (SD) of 0.5, according to the formula, 36 subjects are required. Then, given the importance of the secondary endpoint (WPAI), an improvement of 9.9 ± 25 hours of work time lost (mean=9.9, SD=25) requires 40 subjects. However, we assume a 50% employment rate in the study population and a drop-out rate of 10%, eventually approximately 89 patients will be required ($40/0.5/(1-0.1) = 89$).

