9.7.2 Analyzable population

All subjects who received at least one dose of adalimumab during the study will be included. The main analysis will be conducted on the pooled population, where appropriate, with each individual country analyzed separately as supportive data.

9.7.3**Planned Methods of Statistical Analysis**

All statistical tests will be two-tailed with a significance level of 0.05. Descriptive statistics will be provided. Descriptive analysis will be conducted on all key parameters and presented as mean, standard deviation, minimum, maximum, and median when continuous and as “n” and percent when categorical. Change from adalimumab initiation to 24 weeks will be calculated and evaluated for significant improvements using paired t-tests / ANOVA for parametric and Wilcoxon signed-rank for non-parametric data. Analysis will be also be conducted by severity level (moderate vs severe), disease duration quartile (to compare to prior work) and up to two (2) other subgroups. Cochran-Armitage test of trends or other similar methods may be used to compare categories of subjects.

9.7.4**Primary Endpoint Analysis**

The primary endpoint variable will be the change in HAQ DI score at 24 weeks after the initiation of adalimumab (observed population).

The objective of the primary endpoint analysis will be to demonstrate that treatment with adalimumab improves functioning as measured by the HAQ DI in subjects with RA following treatment initiation. This change will be summarized as the mean and 95% confidence interval and will be tested with a paired t-test.

The primary analysis will be summarized as the mean and 95% confidence interval and will be tested with a paired t-test without adjusting for baseline disease severity. For sensitivity analysis, the mean change in HAQ DI at Week 24 will be analyzed using ANOVA adjusting for baseline disease severity.

9.7.5**Secondary Endpoint Analysis**

The main secondary endpoint variable will be the change in HAQ DI at 12 weeks after the initiation of adalimumab.

The objective of endpoint analysis will be to demonstrate that treatment with adalimumab improves functioning as measured by HAQ DI in subjects with RA compared to baseline.

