9.7.6 Additional Secondary Endpoint Analysis

Additional efficacy analysis includes:

- Change in HAQ DI score at 24 weeks after the initiation of adalimumab, in those patients continuing on adalimumab, compared with those patients not continuing on adalimumab. The mean changes in these two groups will be compared using an independent t-test.
- Healthcare resource utilization will be described using number and percentage within each category (number of consultations, number of procedures received, number of surgeries, number of hospitalizations and length of stay, number of concomitant medications)
- Associations between disease severity and PROs
- Associations between change in disease severity and change in PROs

Exploratory endpoint

Change in patient satisfaction questions at weeks 12 and 24 after the initiation of adalimumab (observed population). These changes will be summarized as number and percentage of each response and compared with Kruskal-Wallis test. Satisfaction will also be dichotomized and analyzed over time with Cochrane-Armitage test for trends.

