6. Knee arthrodesis (fusion)
7. Hip arthrodesis (fusion)
8. Synovectomy
9. Other: _____

* For day surgeries, please input 0 days.

6. Please check any Hylan G-F 20 (Synvisc) injections this patient has received for her/his Rheumatoid Arthritis since the last completed survey.

 No injection performed			
 Yes →	Injection Place	Dosage	Number of shots
	 1 Hip	_____ ml	_____
	 2 Knee	_____ ml	_____

1023259 Real-World Impact of RA
____ + ____
Site number Participant ID

7. Please check any adalimumab (Humira) injection this patient has received for her/his Rheumatoid Arthritis since the last completed survey.		
 No, no injection performed	Dosage	Number of Times
 Yes →	_____ mg	_____
Administration stop date (if stopped)	____/____/____ (DD/MM/YYYY)	
Reason why adalimumab (Humira) is stopped (if stopped):  Progression of disease  Adverse event (AE)  Patient withdrew		

1023259 Real-World Impact of RA
 Site number _____ + Participant ID _____

8. Please record all of the medications this patient has received for her/his Rheumatoid Arthritis since the last completed survey			
Drug Name	Average number of pills per day	Dose strength	Times per month
Disease Modifying Antirheumatic Drug (DMARD)			
 ₁ Auranofin (Ridaura, Myochrysine)	_____	_____ mg	_____
 ₂ Azathioprine (Imuran)	_____	_____ mg	_____
 ₃ Cyclosporine (Sandimmune and Neoral)	_____	_____ mg	_____
 ₄ Hydroxychloroquine (Plaquenil)	_____	_____ mg	_____
 ₅ Leflunomide (Arava)	_____	_____ mg	_____
 ₆ Methotrexate (Rheumatrex, Folex)	_____	_____ mg	_____
 ₇ Minocycline (Minocin, Dynacin and Vectrin)	_____	_____ mg	_____
 ₈ Sulfasalazine (Azulfidine)	_____	_____ mg	_____
 ₉ Others	_____	_____ mg	_____
Anti-inflammatory Drug (NSAID)			
 ₁₀ Ibuprofen (Advil, Motrin, Nuprin)	_____	_____ mg	_____
 ₁₁ Naproxen (Naprosyn, Anaprox, Aleve)	_____	_____ mg	_____
 ₁₂ Celecoxib (Celebrex)	_____	_____ mg	_____
 ₁₃ Aspirin (ASA)	_____	_____ mg	_____

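### The continuer versus non-continuer t-test is filed under efficacy, but it cannot separate drug effect from selection, so its p-value is not evidence that adalimumab works

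*SAP*

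**What the plan says.** SAP 5.3 opens with its purpose: "The objective of the primary endpoint analysis will be to demonstrate that treatment with adalimumab improves functioning as measured by the HAQ DI score". Its first bullet covers the within-patient change, tested with a paired t-test. Its second bullet, reported in Excel Table 3.2, takes the week-24 HAQ DI change "in those patients continuing on adalimumab (responder population) will be compared with those patients not continuing on adalimumab (non-responders", and the p-value of an independent t-test goes in the table.

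Protocol 9.7.6 has the same comparison as the first item under the line "Additional efficacy analysis includes", and states: "The mean changes in these two groups will be compared using an independent t-test". The Abstract and Protocol 9.1 repeat it among the additional secondary analyses.

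SAP 2.3 also classes it as an additional secondary objective, worded as a description. SAP 5.5, the analysis section for those objectives, does not contain it.

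By inclusion criterion 4 (Protocol 9.2.1), every patient starts adalimumab at the baseline visit. The clinician's Early Termination Form (Protocol Appendix K, item 7) gives three reasons for stopping: "Progression of disease", adverse event, and patient withdrawal. The limitations section (Protocol 9.9) says nothing about this comparison.

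**The concern.** The objective concerns whether adalimumab changes functioning. The t-test's null hypothesis is that patients who stayed on the drug and patients who stopped it changed by the same amount. Those are different hypotheses. Both groups were started on the drug, and what separates them is an event after baseline that depends, at least in part, on how the patient is doing. If patients who are getting worse are more likely to stop, the continuers look better whether or not the drug does anything.

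Protocol 7.0 says the results are meant to support pricing and reimbursement. A significant result in a table titled as responders against non-responders, in the same section as the primary result, invites a reading as benefit from staying on treatment. The test cannot support that reading, and nothing in either document warns against it.

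**Working it through.** **Inputs from the documents**
- Protocol 9.5: mean HAQ DI change -0.21, SD 0.5, 89 enrolled, 10% drop-out; sample size set at "alpha of 0.05 and a power of 0.80 in a one-sided test".
- Protocol 9.7.3: "All statistical tests will be two-tailed with a significance level of 0.05". The two-sided level is used below.
- SAP 5.3: meaningful improvement is 0.22 points.
- The link between stopping and HAQ change is not given. It is an assumption here and is varied over a range.

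**The plan's own figures**, with n = [SD × (1.645 + 0.842) / difference]²
- HAQ DI: (0.5 × 2.487 / 0.21)² = 35.06, so 36.
- Work hours: (25 × 2.487 / 9.9)² = 39.44, so 40.
- Enrolment: 40 / 0.5 / 0.9 = 88.9, so 89.

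All three match Protocol 9.5. No size or power is stated for the continuer comparison.

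**What the comparison could detect without selection.** With 80 continuers and 9 stoppers, the standard error is 0.5 × √(1/80 + 1/9) = 0.176. Power for a difference of 0.21 is 22%. A difference of about 0.49 is needed for 80% power.

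**Rejection with no drug effect.** Each patient's change is y = 0 + 0.5z. The chance of stopping is logistic(a + ln(OR) × z), with a set so that 10% stop (8.9 of 89 on average). The test is a pooled two-sample t-test at two-sided 0.05.

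| Odds of stopping per SD of worse change | Rejects | Spurious advantage of continuers (HAQ points) |
|---|---|---|
| 1 (unrelated) | 5% | 0 |
| 1.5 | 20% | 0.20 |
| 2 | 46% | 0.33 |
| 3 | 79% | 0.49 |
| 4 | 90% | 0.58 |

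A second model sets a correlation between HAQ change and a latent tendency to stop, with exactly 9 stoppers. Rejection is 5%, 19%, 37%, 82% and 99% at correlations of 0, 0.2, 0.3, 0.5 and 0.7. If only one third of the 9 stops are outcome-related (correlation 0.5 for those), it is 18%; if two thirds, 50%.

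**Rejection when the drug has an effect of -0.21.** The direction depends on how stopping relates to response.
- *Same effect in both groups, stopping driven by relative position:* the common shift cancels and the rates stay as in the table.
- *Stoppers' recorded value holds only part of the effect:* at correlation 0.3, rejection rises from 37% to 62% (half the effect) or 81% (none of it).
- *Stopping driven by the actual HAQ change:* fewer patients stop when the drug works, so rejection falls to about 18%, 40%, 67% and 79% for odds ratios of 1.5, 2, 3 and 4.

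The same p-value can therefore come from selection alone, from drug effect plus selection, or from a weaker drug with more stopping.

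**The case against.** **Placement may be layout, not intent.** The primary endpoint is consistently the within-patient change with a paired t-test. SAP 5.3 seems to be grouped by instrument, since it also holds the week-12 change and the count of meaningful improvers, both secondary in the protocol. The efficacy line in Protocol 9.7.6 also covers resource-use counts. This is fair: the comparison is not a second primary test. But the efficacy label and the p-value are in the text, SAP 5.5 omits an analysis that SAP 2.3 assigns to that tier, and no caveat appears anywhere.

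**Not every stop reflects a poor outcome.** This stands. The form also lists adverse event and patient withdrawal, the documents give no shares, and with no link the test keeps its 5%. A reader might infer that stopping is simply treatment failure; the form does not support that.

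**The test does react to the drug.** This also stands. A reader might infer that the comparison is blind to drug effect or carries no information. That is exact only when both groups carry the same effect and stopping follows relative position. Otherwise rejection can rise or fall with the effect.

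**The simulation is idealised.** It gives every stopper an evaluable HAQ change. Protocol 9.7.9 says efficacy is not assessed after discontinuation, and Table 1 offers only a termination-visit value. Drop-out also includes patients lost to contact (Protocol 17.0), so evaluable stoppers may be fewer than 9 and the rates lower. The figures are an illustration and not a forecast.

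**Splitting by stop reason is too sparse.** Agreed. Three patients per reason give a 95% half-width of 4.303 × 0.5 / √3 = 1.24 points on a 0 to 3 scale. The follow-up form records a stop date but no reason.

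**Conclusion.** The point holds in this form: the comparison cannot separate drug effect from selection, so its p-value is not evidence of efficacy and should not be presented as such. With no drug effect, rejection runs from 5% to about 90% across odds ratios of 1 to 4, and the spurious difference reaches the planned 0.21 and the 0.22 threshold at an odds ratio between 1.5 and 2. These figures rest on an assumed link between stopping and outcome, 10% stopping, SD 0.5 and complete HAQ data in stoppers.

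A reader might go further and infer that the study's main result is compromised. The documents do not support that. No sample size, decision rule or primary conclusion depends on this test, and the paired t-test has 96% power (two-sided) for a mean change of -0.21 with 80 completers. That figure is power to detect a change from baseline. In a study with no untreated group, the paired test does not by itself attribute the change to the drug either.

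**What to change.** - Move Table 3.2 and its text from SAP 5.3 to SAP 5.5, to match SAP 2.3.
- In SAP 2.3, the moved text, Protocol 9.7.6 and its copies in the Abstract and 9.1, replace the independent t-test with n, mean, SD and 95% CI per group, and drop the p-value.
- In Protocol 9.7.6, take the item out from under the efficacy line.
- List stop reasons as counts only, where recorded.
- Add one sentence: *Groups are defined after baseline by treatment continuation; this comparison is not evidence of the effect of adalimumab.*

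The cost is wording in two documents, one table shell and the loss of one p-value. No new data or patients are needed, and the primary analysis does not change.

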### **3.5.3 Other Co-Variates/Control Variables**

Baseline demographics and clinical characteristics will be used in statistical analysis models.

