#### **5.5 Analysis Plan for Additional Secondary Objectives**

- Descriptive statistics will be presented for post-index overall RA related direct healthcare resource utilization (Excel Table 8)

- Consultations/visits to healthcare professionals for treatment of RA (number of patients with  $\geq 1$  visit; categorized by the treatment department listed in 3.5.4)
- Procedures received when visiting the healthcare professional(s) for treatment of RA (number of patients with  $\geq 1$  procedure; categories listed in 3.5.4)
- surgeries received when visiting the healthcare professional(s) for treatment of RA (number of patients with  $\geq 1$  surgery; categories listed in 3.5.4)
- Hospitalizations in relation to RA (number of patients with  $\geq 1$  admission)
- Length of stay in days (mean, SD, median)
- Concomitant medications taken for RA (number of patients with  $\geq 1$  medication; categories listed in 3.5.4))

- Associations between disease severity (measured by DAS28) and PROs (HAQ DI score, SF-36 domain scales, EQ-5D-3L index, WPAI outcomes) will be analyzed using the bivariate linear regression model (Excel Table 9.1). Separate models will be estimated to identify the association between DAS28 and each of the PROs.
- Additionally, in Excel Table 9.2, separate bivariate liner regression models will be estimated to identify the association between change in DAS28 and change in each of the PROs at 12 and 24 weeks after baseline respectively.

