## 5.6 Analysis Plan for Exploratory Objective

- In Excel Table 10, separate multivariate generalized linear models (GLM) will be estimated to test for the differential changes in primary and secondary efficacy outcomes after baseline, across the subgroups defined by the potential modifiers, including age, gender, baseline severity, and other diagnoses/comorbidities.

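### SAP Table 3.2 gives one unadjusted test of HAQ DI change between continuers and non-continuers; a second, baseline-adjusted estimate and baseline HAQ DI by group should sit beside it

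*SAP*

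**What the plan says.** Protocol 9.7.6 lists, as an additional secondary analysis, HAQ DI change at 24 weeks in patients continuing adalimumab against those not continuing: "The mean changes in these two groups will be compared using an independent t-test". SAP 2.3 repeats the objective, calling the groups responders and non-responders. SAP 5.3 places the analysis under the primary-objective heading as Table 3.2, where the mean "changes in these two groups will be compared using an independent t-test with p-value listed in the table". Mean, SD, range, median and 95% CI are planned for the change. No covariate is named.

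Three other places mention baseline adjustment, and none of them reaches this comparison:

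- SAP 5.3, Table 3.1: "for sensitivity analysis, the mean change will be analyzed using ANOVA adjusting for baseline disease severity, shown by p-value2 in the table". This concerns the overall change from baseline. The severity measure is DAS28, as SAP 5.5 shows ("Associations between disease severity (measured by DAS28) and PROs").
- SAP 5.6, Table 10: exploratory models across modifiers, "including age, gender, baseline severity, and other diagnoses/comorbidities". Neither continuation status nor baseline HAQ DI is listed.
- SAP 3.5.3: "Baseline demographics and clinical characteristics will be used in statistical analysis models". SAP 3.5.2 lists those characteristics, and HAQ DI is not among them.

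SAP 5.2 does not include HAQ DI among the baseline summaries, which are given for all patients and not by continuation group. Protocol Table 1 schedules the HAQ at baseline for every patient.

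**The concern.** Nothing balances baseline HAQ DI between the groups, because membership is settled after baseline by whether treatment continues. HAQ DI runs from 0 to 3. Patients who start worse have more room to improve and, through regression to the mean, may be expected to improve more. If those who stop start from a different level, part of the difference in change may reflect that level and not continuation.

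Two analyses are reasonable, and they can disagree. The plan specifies one, attaches a p-value, and does not plan to display the baseline values a reader would need to judge it. The unadjusted analysis also carries more residual variance than necessary, in a comparison where one group will be very small.

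**Working it through.** **Inputs from the documents.** Mean HAQ DI change −0.21 with SD 0.5, 89 patients, 10% drop-out (Protocol 9.5); 100 patients per country, 13% drop-out (SAP 4); improvement threshold 0.22 (SAP 5.3). For testing, Protocol 9.7.3 says "All statistical tests will be two-tailed with a significance level of 0.05".

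**The plan's own figure.** Protocol 9.5 sizes the study "assuming an alpha of 0.05 and a power of 0.80 in a one-sided test". For a paired change, n = (SD × (z₁₋α + z₁₋β) / δ)² = (0.5 × (1.645 + 0.842) / 0.21)² = 35.06, so 36, as stated. The 40 for work time lost gives 40 / 0.5 / 0.9 = 88.9, so 89, as stated. This confirms that 0.5 is the SD of the within-patient change. Neither figure was set for the two-group comparison.

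**Assumptions not in the documents.** Baseline to week-24 correlation ρ (range 0.3 to 0.8), equal SDs at both times, the same SD of change in both groups, and a usable value for every non-continuer counted. Group sizes: 10% of 89 gives about 80 versus 9; 13% of 100 gives 87 versus 13.

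**Shift in the estimate.** If follow-up depends on baseline with slope ρ and not on group, a baseline gap D produces an expected difference in change of (ρ − 1) × D. The group that starts worse appears to improve more by (1 − ρ) × D.

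- D = 0.30, ρ = 0.5: 0.5 × 0.30 = 0.15, about two thirds of 0.22 (0.15 / 0.22 = 0.68).
- D = 0.30, ρ from 0.3 to 0.8: 0.21 down to 0.06.

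If the groups would have changed in parallel whatever their starting level, this term is absent from the change score, and the adjusted model is the one displaced.

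**Both assumptions by simulation.** 80 versus 9, ρ = 0.5, baseline gap 0.5, no true group effect, two-sided 0.05, 5,000 runs each:

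| What generates follow-up | t-test rejects | Adjusted model rejects |
|---|---|---|
| Depends only on baseline | 28% | 6% |
| Groups change in parallel | 5% | 35% |

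At ρ = 0.7 the figures are 14% and 5% in the first row, and 5% and 14% in the second.

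**Precision.** Var(change) = 2s²(1 − ρ). The adjusted residual variance is s²(1 − ρ²). The ratio is (1 + ρ)/2. At ρ = 0.5 it is 0.75, and the SD falls from 0.50 to 0.5 × √0.75 = 0.433. The standard error falls by 19% at ρ = 0.3 and by 5% at ρ = 0.8, without imbalance. Two-sided power from the noncentral t, 80 versus 9:

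| True difference | t-test | Adjusted, ρ = 0.3 | ρ = 0.5 | ρ = 0.8 |
|---|---|---|---|---|
| 0.21 | 22% | 31% | 28% | 24% |
| 0.30 | 39% | 55% | 50% | 43% |
| 0.40 | 61% | 80% | 74% | 66% |
| 0.50 | 80% | 94% | 90% | 84% |

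For a difference of 0.30 at ρ = 0.5, power goes from 52% to 64% with 87 versus 13. With only 6 usable non-continuers beside 80 continuers it goes from 29% to 37%, and with 4 from 21% to 27%.

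**The case against.** The strongest objection is that baseline adjustment is not neutral in non-randomised groups. The change score and the adjusted model rest on different assumptions that cannot be tested here, and the documents favour neither. The simulation shows the error reversing with the assumption. This stands, and it rules out replacing the t-test. It does not rule out showing both estimates.

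Second, the data may be thinner than assumed. Protocol 9.7.9 and SAP 3.5.5 say efficacy is not assessed after adalimumab stops, and Protocol 17.0 says nothing further is collected after drop-out. What remains is the HAQ at the early termination visit in Protocol Table 1, taken at another time. Drop-out also includes patients who withdraw or cannot be reached. Nine usable non-continuers is therefore probably optimistic, and the power gain smaller. This also stands.

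Third, the analysis is an additional secondary objective worded as descriptive, with no sample size attached. True, but it still carries a p-value.

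Four stronger readings are tempting and are not supported:

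- A reader might infer that the t-test ignores baseline HAQ DI. It does not: the outcome is a change, so each patient's baseline is subtracted. Covariate adjustment is what is absent.
- A reader might infer that any baseline difference biases the test. That holds only if change depends on the starting value.
- A reader might take this for the only group comparison of HAQ DI. Protocol 9.7.3 also analyses by severity level, and Protocol 9.7.8 and SAP 5.6 test changes across subgroups.
- A reader might take SAP 3.5.3 as a promise to adjust for baseline HAQ DI. The SAP treats HAQ DI as an outcome (3.5.1), not as one of the baseline characteristics it lists in 3.5.2.

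**Conclusion.** The point holds as a modest improvement. The comparison of continuers with non-continuers rests on one unadjusted test between groups formed after baseline. No planned analysis adjusts it for baseline HAQ DI, and the SAP text does not plan to show baseline HAQ DI by group (the table shells are a separate workbook, not part of these documents).

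The two reasonable estimates would differ by 0.15 for a gap of 0.30 at ρ = 0.5, and by 0.06 to 0.21 over ρ from 0.8 to 0.3. The documents do not say which would be the unbiased one. Adjustment would add about 10 points of power for a 0.30 difference at ρ = 0.5 with 80 versus 9. Power for 0.21 stays low either way. The gap and ρ are assumed, and the group sizes are inferred from the drop-out rates. The primary paired t-test is not affected.

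**What to change.** In SAP 5.3 (Table 3.2) and Protocol 9.7.6:

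- Keep the independent t-test.
- Add, as a pre-specified second estimate, the difference in HAQ DI change from a linear model with continuation group and baseline HAQ DI, with its 95% CI.
- Show baseline HAQ DI (n, mean, SD) by group in the same table.
- Label the comparison descriptive, since the groups are not randomised and form after baseline.
- State which HAQ DI value, taken when, represents a patient who stopped. Both estimates need this.

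The cost is about one SAP sentence for the second estimate, one model term and one degree of freedom. Baseline HAQ DI is already collected. The downside is a second estimate that may disagree with the first; the text should say that each answers under a different assumption. Adjustment does not remove confounding by the reasons for stopping, and it does not supply a true week-24 value for patients who stopped.
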